### Data Collection:

Cutaneous toxicity will be assessed at baseline, fraction 15 of XRT and 2 - 5 weeks, 7 - 12 weeks, and 12 – 18 months post XRT by objective ultrasound measurements (UTC). Photographs of the treated breast or chest wall as well as the contralateral breast will also be taken. Documentation of the UTC and photographs will be kept in electronic format for reference. For each visit after the baseline (after treatment has begun), cutaneous toxicity will be assessed by a clinician. Participants will be seen by the investigator in follow up at the third and/or fourth visits and at the fifth visit and an investigator dictation will be performed.

Patients who have had a mastectomy and plan for permanent breast reconstructive surgery after radiation will be assessed within one month of their permanent reconstructive surgery and 5 - 7 months following their surgery using the same procedures as described above. It is highly variable as to when reconstruction will occur. If these time points do not fall within the time frame for the regular study visits, additional study visits will be added for these patients.

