**PI: [name]**  
**IRB00047240**  
**NCT03167359**

**Version 04/01/2021**

We conducted a prospective study to assess the safety and feasibility of delivering 15 fractions of simultaneous integrated boost (SIB) radiotherapy for definitive breast cancer treatment.

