**Data**

The SIB dataset was queried, and after exclusion and inclusion listed in the selection diagram file. Total 75 cases were included.

Selection and Exclusion Criteria	Sample Size	Excluded
SIB radiotherapy for breast cancer cases	75	-

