**Outcome and definition**

1. Skin Thickening Ratio (STRA) Baseline
2. Skin Thickening Ratio (STRA) at 1 year
3. Change in Skin Thickening Ratio (STRA) from Baseline to 1 year
4. Overall Survival was defined as months from the date of radiation ended to death or last seen at Emory.
5. Local Recurrence-free Survival (LRFS) was defined as months from the date of radiation ended to local recurrence or last seen at Emory.
6. Distant Recurrence-free Survival (DRFS) was defined as months from the date of radiation ended to distant recurrence or last seen at Emory.

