### **Statistical Analysis**

Statistical analysis was conducted using SAS Version 9.4, and SAS macros developed by Biostatistics and Bioinformatics Shared Resource at Winship Cancer Institute. Descriptive statistics for each variable were reported. Association between variables of interest and the study cohort were examined using ANOVA for categorical variables and Pearson correlation coefficient for continuous variables. Multi-linear regression between variables of interest and the study outcomes was examined. Variables were selected based on statistical significance on univariate analysis, while accounting for multicollinearity and removing variables with high rates of missing data.

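### The SAP does not specify baseline STRA as a covariate when 1-year STRA or change in STRA is the outcome

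*SAP*

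**What the plan says.** The SAP section Outcome and definition opens with three STRA outcomes: "Skin Thickening Ratio (STRA) Baseline", "Skin Thickening Ratio (STRA) at 1 year" and "Change in Skin Thickening Ratio (STRA) from Baseline to 1 year". The other three outcomes there are survival and recurrence times, so the linear model must be meant for STRA.

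The SAP section Statistical Analysis gives that model in one sentence: "Multi-linear regression between variables of interest and the study outcomes was examined". The variables of interest are not listed. On entry to the model it says "Variables were selected based on statistical significance on univariate analysis", with further allowance for multicollinearity and missing data. No term is forced in. Baseline STRA appears only as an outcome.

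The baseline value should be on file. The protocol, under Data Collection, schedules ultrasound from the start: "Cutaneous toxicity will be assessed at baseline, fraction 15 of XRT and 2 - 5 weeks, 7 - 12 weeks", with a last window at 12 to 18 months. The SAP section Data reports "Total 75 cases were included". It does not say how many of these patients have STRA at both times.

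**The concern.** When an outcome is measured before and after treatment, the baseline value is usually the strongest single predictor of the later one. Leaving it out of the 1-year model leaves that variation in the residual. Using the raw change instead fixes the baseline coefficient at 1, whatever the data say. Either choice can waste information, and there are at most 75 patients.

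There is also a question of interpretation. If change is correlated with baseline, a factor that happens to be unbalanced at baseline will seem to predict change. Selection by univariate significance favours such factors. At stake is which patient or treatment factors are reported as related to skin thickening, and with what precision.

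**Working it through.** **Inputs.** The only number from the documents is N = 75 (SAP, Data). Neither document gives an SD, effect size, power figure or baseline-to-1-year correlation for STRA, so there is no planned figure to reproduce. Assumed here:
- the correlation *r* (0.3, 0.5, 0.7);
- the SD ratio *k* = SD(1 year)/SD(baseline) (1, 1.5, 2);
- complete STRA data in all 75.

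**Step 1: residual variances, with the baseline SD set to 1.**
- Unadjusted 1-year value: *k*²
- Unadjusted change: 1 + *k*² − 2*rk*
- 1-year value or change, adjusted for baseline: *k*²(1 − *r*²)

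**Step 2: adjusted against unadjusted change.** The ratio is *k*²(1 − *r*²)/(1 + *k*² − 2*rk*), which becomes (1 + *r*)/2 when *k* = 1.

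| *k* | *r* = 0.3 | *r* = 0.5 | *r* = 0.7 |
|---|---|---|---|
| 1 | 0.65 | 0.75 | 0.85 |
| 1.5 | 0.87 | 0.96 | 0.998 |
| 2 | 0.96 | 1.00 | 0.93 |

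No entry exceeds 1, because least squares estimates the coefficient that the change score fixes. At *k* = 1 the standard errors fall by 19%, 13% and 8% (1 − √ratio). Seventy-five adjusted patients are then worth 75/0.65 = 115, 75/0.75 = 100 and 75/0.85 = 88 analysed by unadjusted change.

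**Step 3: adjusted against the unadjusted 1-year value.** The ratio is 1 − *r*² for any *k*: 0.91, 0.75 and 0.51, a saving of 9%, 25% and 49%.

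**Step 4: power, for illustration.** Assume two equal groups of 37.5, a true difference of 0.5 baseline SD, *k* = 1 and two-sided 5%. Power is Φ(0.5/(σ√(2/37.5)) − 1.96). With σ = √(2(1 − *r*)) for change it is 0.448, 0.581 and 0.798. With σ = √(1 − *r*²) for the adjusted model it is 0.622, 0.705 and 0.858.

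**Step 5: correlation of baseline with change.** This is (*rk* − 1)/√(1 + *k*² − 2*rk*).
- *k* = 1: −0.59, −0.50, −0.39
- *k* = 1.5: −0.36, −0.19, +0.05
- *k* = 2: −0.21, 0, +0.27

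The sign depends on *k*.

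**Step 6: a factor with a 0.5 SD baseline difference and no true effect, *k* = 1.** Two cases give errors of equal size, (1 − *r*) × 0.5 = 0.35, 0.25 and 0.15 SD:
- If the imbalance is chance, unadjusted change shows that spurious difference and the adjusted model does not.
- If the groups differ stably, unadjusted change is unbiased and the adjusted model shows it.

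**Step 7: would the screen admit baseline STRA anyway?** Suppose it were a candidate, with a 0.05 threshold (the SAP gives none). The chance of passing is about Φ(|atanh ρ|√72 − 1.96), where ρ is its correlation with the outcome. For change at *k* = 1 this is 1.00, 0.997 and 0.93. For the 1-year value (ρ = *r*) it is 0.75, 0.997 and 1.00.

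**The case against.** Several points weigh against the concern.

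**Silence is not exclusion.** A reader might infer that the models were fitted without baseline STRA. The documents do not support that. The variables of interest are unlisted, and step 7 shows that baseline STRA would often pass the screen if it were a candidate. It is also an inference that the predictors are patient factors. What stands is that the SAP does not specify the term and leaves its entry to a screen.

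**Change is the protocol's own quantity.** The first item under Secondary Outcome Measures concerns changes in ultrasound measurements. That is a good reason to keep reporting change. It is no reason to leave baseline out: with baseline in the model, the 1-year and change outcomes give identical factor coefficients.

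**Adjustment can itself mislead.** The SAP describes its study thus: "We conducted a prospective study to assess the safety and feasibility of delivering 15 fractions of simultaneous integrated boost (SIB) radiotherapy". No randomised comparison appears. Baseline precedes radiation but follows surgery, and often chemotherapy, so factors such as prior chemotherapy or surgery type may already have shifted it. The second case in step 6 then applies, and the error is as large as the one adjustment would cure. This objection stands in full. It is why both models should be shown.

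**The gain may be small.** A reader might take 15% to 35% as the full range, or hold that measurement error alone makes change fall with baseline. Neither follows. The range assumes equal SDs, and the correlation reflects any imperfect agreement between the two times, including real differences in response. It can be zero or positive.

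**Part of the information is already there.** Baseline STRA is an outcome in its own right. With the same patients and covariates, the change coefficient equals the 1-year coefficient minus the baseline one. But the screen may select different covariates for each outcome, so the SAP does not guarantee this comparison.

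**Conclusion.** The point holds as a gap in specification. Baseline STRA is scheduled for collection and listed as an outcome, but the SAP does not name it as a covariate for 1-year STRA or change in STRA. Apart from one degree of freedom, the unadjusted models never have the smaller residual variance. Against change, the saving is 35%, 25% and 15% at *r* = 0.3, 0.5 and 0.7 with equal SDs, and can be near zero if the SD grows after radiation. Both *r* and the SD ratio are assumptions.

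The documents do not show that the fitted models lacked a baseline term, that the change results are biased, or that adjustment would remove bias for non-randomised factors.

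STRA is not defined in either document. I take it to be the ultrasound skin-thickness measure, which belongs to a secondary outcome. The primary outcomes are graded skin toxicity, arm lymphedema and brachial plexopathy, and the primary toxicity conclusion does not depend on this point. It is an inexpensive improvement worth making.

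**What to change.** Amend the SAP section Statistical Analysis as follows:
- List the variables of interest.
- Make the main STRA model the regression of 1-year STRA on those factors, with baseline STRA forced in regardless of the univariate screen. A second baseline-adjusted model for change would be redundant.
- Report the unadjusted change model beside it, with mean change and its 95% interval.
- State how many of the 75 patients have both measurements.
- Say in advance that where the two models disagree on a factor, its effect is called inconclusive.

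The cost is a few lines of text, one re-run and one degree of freedom. No new data are needed. The drawback is that, for factors that may already shift baseline, the two models answer different questions, and some factor effects will be left open.

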# Study Design:

Eighty breast cancer patients with Stage 0-III BrCA treated with breast conserving surgery or mastectomy and clear margins will be recruited to the study. Patients must have **one or more** of the following characteristics and be eligible for breast or chest wall with or without regional nodal radiotherapy:

1. Prior Chemotherapy for Breast Cancer

2. >25 cm of breast separation (the largest distance on an axial slice of the planning CT simulation scan between the entry and exit points of the radiation beam on the body)

- 3. Non-Caucasian Race
- 4. 4.
- 5. Requiring regional nodal irradiation without evidence of N3 disease

Because the above characteristics in isolation have been correlated with heightened levels of skin toxicity and/or were under-represented in previous trials of hypofractionated XRT, any patient fulfilling one of the above criteria, will be approached for enrollment in the study.

Males will be excluded.

To protect against possible side effects of radiation, women who are pregnant or nursing a child may not take part in this study.

Patients who have not received chemotherapy may start XRT up to 16 weeks after lumpectomy surgery. Patients who receive adjuvant chemotherapy after lumpectomy may start XRT up to 7 weeks after their last cycle of chemotherapy.

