Information regarding disease characteristics (including stage, tumor size, grade), patient demographics (including age, race, co-morbidities, social history, body mass index), systemic treatment (including hormone therapy, systemic therapy), surgical treatment, radiation treatment, and clinical outcomes (local control, distant metastasis, survival, and treatment complications) will be collected and recorded.

Patients may also be asked to participate in a long term assessment between 1 and 10 years where they will complete the same study procedures as outlined above. Patients will be compensated \$50.00 for completing this visit.

A follow up phone survey will be taken between 18 months and 10 years after treatment. Using the same scales as in the study visits, the patients will be asked to rate their fatigue level, breast pain, how happy they are with the look of their breast and how different their radiated breast is from their non-radiated breast. They will also be asked if they are on any hormonal treatment for breast cancer and if so, the date they started. We will obtain verbal consent for this survey from patients who completed this study before the follow up phone survey was originally approved on 9/24/2013.

Assuming 10% of patients dropout, 53 patients requiring breast only radiation will be enrolled (2-3 patients per month) to yield a total of 50 patients.

An additional 33 patients requiring regional nodal irradiation and breast or chest wall radiation will be enrolled. Assuming 10% of patients dropout, 33 patients of these patients will be enrolled (2-3 patients per month) to yield a total of 30 patients receiving regional nodal irradiation and breast or chest wall radiation.

In patients undergoing regional nodal irradiation, arm measurements will be taken of the ipsilateral and contralateral upper extremity at baseline, 7 - 12 weeks, and 12 – 18 months post XRT by a licensed lymphedema therapist or study staff trained by a licensed lymphedema therapist. These patients will also be assessed for brachial plexopathy using RTOG grading toxicity, LENT/SOMA grading toxicity, and a modified version of a validated questionnaire to assess symptoms of brachial plexopathy at baseline and 7 - 12 weeks, and 12 – 18 months post XRT.[24] If a patient develops RTOG or LENT/SOMA Grade 3 toxicity, an objective measurement (MRI and/or nerve conduction studies) of brachial plexopathy will be employed.

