### Secondary Outcome Measures:

- 1. Rate of cutaneous toxicity, as measured by changes in cutaneous measurements, acquired vis ultrasound tissue characterizations (UTC)
- 2. Local control will also be assessed through routine physical examination, annual screening mammograms, ultrasound, and biopsy to confirm local recurrence.
- Blood will be analyzed for biomarkers and inflammatory markers including(tumor necrosis factor (TNF)-alpha, soluble TNF receptor 2 (sTNFR2), interleukin (IL)-6, IL-1ra, and C - reactive protein (CRP) as well as genetic factors to determine if they are associated with development of cutaneous toxicity.
- 4. Change in Multidimensional Fatigue Inventory (MFI) Score

[Time Frame: Baseline, End of Follow Up (Up to 18 months)] [Safety Issue: No]

The Multidimensional Fatigue Inventory (MFI) is a 20-item self-report instrument designed to measure fatigue. Scores range from 20 to 100. The higher the score, the more fatigued.

5. Change in Pittsburgh Sleep Quality Index (PSQI) Score

[Time Frame: Baseline, End of Follow Up (Up to 18 months)] [Safety Issue: No]

The PSQI is a self-rated questionnaire which assesses sleep quality and disturbances over a 1-month time interval. Scores range from 0 to 21. A score of less than or equal to 5 is associated with good sleep quality. A score greater than 5 is associated with poor sleep quality.

6. Change in Perceived Stress Scale (PSS) Score

[Time Frame: Baseline, End of Follow Up (Up to 18 months)] [Safety Issue: No]

The PSS is a self-reported instrument used to measure the perception of stress. Scores range from 0 to 40. Score of 20 or higher are considered high stress.

7. Change in Patient Reported Outcomes Measurement Information System (PROMIS) Fatigue Short Form Score

[Time Frame: Baseline, End of Follow Up (Up to 18 months)] [Safety Issue: No]

The PROMIS Fatigue questionnaire is a self-report tool used to evaluate frequency, duration, and intensity of fatigue over the past seven days. Scores range from 7 to 35. The higher the score, the more fatigue.

8. Change in an Inventory of Depressive Symptomatology-Self Reported (IDS-SR) score

[Time Frame: Baseline, End of Follow Up (Up to 18 months)] [Safety Issue: No]

The IDS-SR is a self-reported measure in which participants rate the frequency of depression symptoms within the past seven days. Scores range from 0 to 84, with higher score reflecting greater severity of depressive symptoms.

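### Local and distant recurrence-free survival in the SAP do not count death as an event, so each will overstate recurrence-free survival if any patient dies without the named recurrence.

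*SAP*

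**What the plan says.** The SAP section Outcome and definition lists three time-to-event outcomes, all starting at the end of radiation.

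- Item 4: "Overall Survival was defined as months from the date of radiation ended to death or last seen at Emory".
- Item 5, local recurrence-free survival (LRFS): "months from the date of radiation ended to local recurrence or last seen at Emory".
- Item 6, distant recurrence-free survival (DRFS): "months from the date of radiation ended to distant recurrence or last seen at Emory".

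Death is named in item 4 and in neither of the others. The SAP section Statistical Analysis mentions descriptive statistics, ANOVA, Pearson correlation and linear regression. It names no time-to-event estimator, censoring rule or competing-risk rule. The SAP section Data gives the analysis set: "Total 75 cases were included".

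In the protocol, local disease is a secondary outcome framed as control, not as a survival composite: "Local control will also be assessed through routine physical examination, annual screening mammograms, ultrasound, and biopsy to confirm local recurrence" (Secondary Outcome Measures, item 2). Under Data Collection, "clinical outcomes (local control, distant metastasis, survival, and treatment complications) will be collected and recorded". The protocol gives no rule for death without recurrence either.

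**The concern.** The label and the definition disagree. Recurrence-free survival ordinarily means being alive and free of the recurrence, so death ends it. Under items 5 and 6 a patient who dies without the named recurrence has no event. Her time stops when she was last seen, exactly as if she had stopped attending.

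Two consequences follow. A reader will take the reported figures for a composite that they are not. And since all three outcomes share a starting date, a true recurrence-free survival can never exceed overall survival, whereas these two can.

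Such deaths are foreseeable. The study enrols "Eighty breast cancer patients with Stage 0-III BrCA treated with breast conserving surgery or mastectomy and clear margins", and a patient may die of distant disease without any local recurrence. She would then count as locally recurrence-free up to her last visit.

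**Working it through.** The documents state no LRFS or DRFS rate and no number of recurrences or deaths, so there is no planned figure to reproduce. What can be checked is the direction of the effect and its size per death.

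**Inputs.** N = 75 (SAP, Data). Assumed for illustration: 3 local recurrences, k deaths without local recurrence, no other censoring, and the 3 patients with recurrence alive.

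**Step 1. LRFS as written, with deaths censored (product-limit estimate).**
- All recurrences before any death: (74/75)(73/74)(72/73) = 72/75 = 96.0%.
- All deaths before any recurrence: only 75 − k remain at risk, which gives (72 − k)/(75 − k). For k = 5 this is 67/70 = 95.7%.

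**Step 2. LRFS with death as an event.** (72 − k)/75. For k = 5 this is 67/75 = 89.3%.

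**Step 3. Overall survival in the same example.** (75 − k)/75. For k = 5 this is 70/75 = 93.3%.

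| k | LRFS as written | LRFS with death as event | Excess (points) | Overall survival |
|---|---|---|---|---|
| 0 | 96.0% | 96.0% | 0 | 100% |
| 1 | 95.9–96.0% | 94.7% | 1.3 | 98.7% |
| 3 | 95.8–96.0% | 92.0% | 3.8–4.0 | 96.0% |
| 5 | 95.7–96.0% | 89.3% | 6.4–6.7 | 93.3% |
| 10 | 95.4–96.0% | 82.7% | 12.7–13.3 | 86.7% |

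The excess is at most k/75, about 1.3 points per death, and only slightly less when deaths come first. With 5 deaths, LRFS as written (95.7–96.0%) is above overall survival (93.3%), which a recurrence-free survival cannot be. The same arithmetic applies to DRFS, where k counts only deaths without a recorded distant recurrence.

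**Step 4. If local control is the target.** Assume constant hazards. Take the recurrence hazard from the 2.8% local recurrence at 3 years that the protocol's Background gives for the institution's 25-fraction regimen: λr = −ln(0.972)/3 = 0.00947 per year. Assume a 10% five-year risk of death without recurrence: λd = −ln(0.90)/5 = 0.02107 per year.
- Kaplan-Meier with deaths censored, at 5 years: exp(−5λr) = 95.4%.
- Death as an event: exp(−5(λr + λd)) = 0.954 × 0.90 = 85.8%.
- Cumulative incidence of local recurrence: λr/(λr + λd) × (1 − 0.858) = 0.310 × 0.142 = 4.4%, so 95.6% have had no local recurrence.

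Against the composite, the censored figure is 9.5 points too high (before rounding). Against local control, it is 0.2 points too low.

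**The case against.** Several points on the other side are sound.

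- Censoring is inferred. The SAP states no censoring rule and no survival estimator, and that gap is wider than these two definitions. The contrast with item 4 still makes censoring the natural reading. If the analysts did count deaths as events, the written definitions are wrong and need the same correction.
- No deaths are reported. If no patient died without the named recurrence, the overstatement is zero.
- The two outcomes are not equally exposed. A patient who dies of distant disease will normally already have a DRFS event, so DRFS is affected only by deaths without a recorded distant recurrence.
- The consequences are limited. The primary outcomes are cutaneous toxicity and, in patients receiving nodal irradiation, lymphedema and brachial plexopathy. No test, threshold or stopping rule depends on LRFS or DRFS.

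A reader might also infer that the regimen's disease control will look better than it is. The documents do not support that. The protocol's own outcome is local control, and for that quantity censoring deaths makes control look slightly worse, as step 4 shows. What is overstated is the composite of survival and freedom from recurrence.

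The mismatch between label and definition, and the absence of any rule for death without recurrence, stand after all of this.

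**Conclusion.** As written, items 5 and 6 are not recurrence-free survival. If any patient dies without the named recurrence, the reported figure will be too high by roughly 1.3 percentage points per such death among 75 patients, and it can exceed overall survival. LRFS is the more exposed.

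This rests on deaths being censored at the last-seen date. The per-death figure also rests on few recurrences and little other loss to follow-up.

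A reader might combine the 2.8% three-year local recurrence with a guessed 3% to 10% of deaths (0.972 × 0.97 = 0.943; 0.972 × 0.90 = 0.875) and call LRFS 3 to 10 points too high. That range merely restates the guessed death rate, and the 2.8% belongs to a different, 25-fraction regimen. The documents fix the direction and the size per death, but not a total. The definitions should be corrected, although no primary conclusion depends on them.

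**What to change.** In the SAP, Outcome and definition, items 5 and 6, do one of the following:

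1. Define LRFS and DRFS as time from the end of radiation to the named recurrence or death from any cause, whichever comes first, and censor only patients alive without that recurrence.
2. Rename them time to local recurrence and time to distant recurrence, and report cumulative incidence with death as a competing event.

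In either case, report the cumulative incidence of local recurrence, with death as a competing event, for the protocol's local control outcome. Name the estimator and the censoring rule in Statistical Analysis, and state how many patients died without each recurrence, so that readers can see whether the choice matters.

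The cost is two definition lines, a sentence on method and a re-run. Overall survival already needs the death dates, so no new data are required. The drawback is that LRFS and DRFS under option 1 may be slightly less favourable.
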